5.2.5 Prior and Concomitant Medications and Therapies

Prior and concomitant medications will be coded using the World Health Organization Drug Dictionary and the Anatomical Therapeutic Chemical (ATC) classification system. Coding will include the drug class and generic drug name.

All prior and concomitant medications will be listed, including verbatim descriptions and coded terms.

Prior medications, concomitant medications during the initial treatment period (through the day prior to Visit 9 [“Month 6”] infusion), concomitant medications from Visit 9 (“Month 6”) through the day prior to Visit 12 (“Month 9”), and concomitant medications from Visit 12 (“Month 9”) through Visit 15 (“Month 12”) will be summarized according to treatment received during the period using the number and percentage of subjects reporting any medication use, and the number and percentage of subjects reporting each drug class and generic drug name. For each subject, multiple records of the same medication will be counted once within a drug class and generic drug name.

Prior and concomitant medications will be presented for the safety population.

5.2.6 Medical History

Past and current medical conditions including disease history will be recorded at screening and will be coded using MedDRA version 19.0. The number and percentage of subjects reporting any medical history and any medical history for each system organ class and preferred term will be summarized by treatment group from the initial treatment period. Subjects will be summarized only once at any level (any history, system organ class, and preferred term) if they have multiple reports at the level. Treatment group differences in the reporting of any medical history will be assessed using the Pearson Chi-square test. Data will be presented for the safety population and FAS.

5.3 Efficacy Analysis

All efficacy analyses will be performed on both the FAS and PP populations.

5.3.1 Primary Efficacy Variable

The modified ICARS total score from the central rater (with speech domain scores from local raters) at baseline and each follow-up visit, and the change and percent change from baseline to each follow-up visit, will be summarized using descriptive summary statistics by treatment group.

The primary efficacy variable, change from baseline to follow-up (Visit 6 [“Month 3”] and Visit 9 [“Month 6”]) in mICARS total score (described above), will be analyzed using a mixed model repeated measures (MMRM) analysis, with the baseline mICARS value as covariate and five fixed effects (treatment, age [6 to <10 years, ≥ 10 years], sex, region, visit) and one interaction term (treatment-by-visit). The treatment effect, together with the associated two-sided 95% CI and p-value will be calculated. Unstructured covariance matrices will be used. Model effect estimation will be based on restricted maximum likelihood (REML). The region-by-treatment interaction can be tested in a separate model and if a significant interaction is found, then a forest plot will be used to present the region-specific treatment effects and associated 95% confidence intervals.

The primary MMRM analysis will assume missing at random (MAR) as a means of handling missing data.

Sensitivity analyses of these primary analyses will consist of ANCOVA at Visit 9 (‘‘Month 6’’) with missing data imputed using multiple imputations as described in [Section 5.1.3](#), LOCF, and OC. The results from each of the sensitivity analyses will be compared to the primary MMRM analysis.

When applying the multiple imputation methods describe in [Section 5.1.3](#), the regression method will be used, and the imputation model will be the same as the analysis model, based on the factors treatment, sex, age (category), region, and baseline mICARS; the pattern of missing data will be essentially monotonic since none of the factors used in the model are expected to be missing. One hundred iterations of the model will be run, and the results will be combined with SAS PROC MIANALYZE. For Multiple Imputation Method #2, multiple imputation based on subjects taking the same treatment will be applied first to the missing data due to COVID-19 related restrictions, and then Jump to Reference will be applied to the remaining missing data.

For the extension treatment period, the change from baseline will be the change from the last assessment prior to first infusion in the study except for the placebo subjects who switch to EDS-EP at Visits 9 and 12 (‘‘Month 6’’ and ‘‘Month 9’’, respectively). For these subjects who are switched, the baseline will be the assessment just prior to the switch. The change will be summarized for Visit 12 (‘‘Month 9’’) and Visit 15 (‘‘Month 12’’), using LOCF and OC. Because

of the small sample size and the switch from placebo to EDS-EP, no formal statistical comparisons of treatment groups will be made.

For the FAS only, the mean mICARS score will be plotted over time during the initial treatment period with separate trend lines for each of the three treatment groups. This type of plot will be repeated for mean mICARS score and mean change from baseline in mICARS score over the entire study, with separate trend lines for the seven possible dosing schemes.

For the placebo subjects who switched to EDS-EP at Visit 9 (“Month 6”), the change seen during the initial treatment period, and the change between Visit 9 (“Month 6”) and Visit 15 (“Month 12”) will be compared with a paired t-test or a non-parametric equivalent. A comparison of the change over 3 months of placebo against 3 months of treatment will also be done using the first 3 months for the subjects who switch at Visit 9 (“Month 6”) and those who switched at Visit 12 (“Month 9”).

Sensitivity Analyses

The full ICARS will be analyzed using the same methods as for the primary analysis of mICARS. The nominal p-value will be presented, and no adjustments for multiplicity will be made.

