A-T NEST (in selected centers)			X				X				X
RBC osmotic resistance (t)	X				X						
Special Laboratory Tests (m)										X(f)	
Hemolysis Panel (s)	X	X			X	X					
EDS end product sample (u)	X		X	X	X		X	X	X		
Prior/Concomitant Treatments	Throughout the duration of the study										
Adverse Events	Throughout the duration of the study										X

a) Efficacy evaluations on Month 6 (Visit 9) will be used as the Endpoint assessments for all efficacy measures.

Clinical Study Protocol IEDAT-02-2015

EDS in Ataxia Telangiectasia Patients

Version 1.0, 09May2015; Version 2.1, 16Nov2015; Version 3.0 (Amend. 1), 01Feb2016; Version 3.1 (Amend. 2), 28Apr2016; Version 3.2 (Amend. 3), 25May2016; Version 4.0 (Amend. 4), 29Nov2016; Version 5.0 (Amend. 5, Site-specific), 20Sep2017; Version 6.0 (Amend. 6), 29Sep2017; Version 7.1 (Amend. 7.1), Final 13 March 2018, Version 8.0 (Amend. 8.0), Final 23 April 2018; Version 10.0 (Amend. 10), Final 16 April 2019; Version 11.0 (Amend. 11), Final 24 Jun 2020

- b) Month 6 (Visit 9; Endpoint) evaluations should be performed for all patients that complete the Initial Treatment Period, as well as patients that discontinue prematurely; these evaluations will be used as the baseline assessments for the double-blind, Extension Treatment Period.
- c) Procedures to be done before (Pre) and after (Post) the EDS-EP infusion.
- d) These evaluations will be repeated only if abnormalities requiring follow-up were noted at the Screening evaluation; results from the repeat assessments must be available at baseline to confirm eligibility before the patient can be randomized to treatment.
- e) Routine laboratory assessments to include complete hematology, biochemistry, and urinalysis.
- f) Special laboratory tests include HbA1c, CD4+ lymphocytes count, α -fetoprotein (not repeated at baseline), CRP, and RBC antibodies (IgG, IgM, Qualitative Direct Coombs test – not repeated at baseline).

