7.3 Study Rationale

Study IEDAT-02-2015 is an international, multi-center, one-year, randomized, double-blind, placebo-controlled, Phase III study to assess the effect of two non-overlapping dose ranges of EDS-EP on neurological symptoms of patients with AT. The primary efficacy endpoint will be at the 6-month assessment. Patients completing the initial 6-month treatment period will be eligible to continue treatment in a 6-month, double-blind, placebo-controlled extension performed to evaluate long-term safety and provide preliminary evidence of a long-term effect on symptoms of AT.

Rationale for Using the EDS in Treating AT Patients

AT is considered a *rare disease* by the Office of Rare Diseases of the National Institutes of Health (US), as well as by *Orphanet*, the consortium of European partners. There is no marketed drug approved to treat AT, and there is no treatment available that slows down or stops the progression of AT patients to early debilitating disability and mortality. Symptomatic, preventive, and supportive management of the key disabilities and symptoms of the disease has provided limited benefit. Immune deficiencies are managed by administration of immunoglobulins, and infections are managed by both preventive and symptomatic use of antibiotics. Developmental deficiencies are managed by physical therapies, education, or targeted treatments (Hoche et al, 2012).

Neurological degeneration is the major contributor to the severe outcome of the disease. The progression of the neurologic problems is currently unstoppable. Anti-parkinson and antiepileptic drugs provide limited benefit in the management of extrapyramidal symptoms. The serendipitous discovery of the benefit of short-term betamethasone in a patient with AT (Buoni et al, 2006), and further pilot, uncontrolled, short-term treatment trials in small numbers of patients have suggested that betamethasone at doses of 0.03 mg/kg, but not 0.01 mg/kg, given for a short period has beneficial effects on the neurological impairment of AT patients (Russo et al, 2009; Broccoletti et al, 2008). Treatment discontinuation in these studies was accompanied by the reappearance of symptoms, suggesting that long-term administration may be required to preserve the benefit.

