After completion of the IV infusion of the study treatment, a physical examination and vital signs will be performed (1-2 hr after infusion). At Month 3 (Visit 6), a complete set of efficacy (ICARS, CGI-C, CGI-S, VABS, and QoL) and safety (vital signs, ECG, routine laboratory tests, physical and neurological examinations) evaluations will be performed, and a hemolysis panel will be done pre- and post-infusion. In addition, the diverted blood samples will be collected for mini-ATM detection at Months 2 and 6.

The final evaluations for the Initial Treatment Period will take place at Visit 9 (Month 6 or at early termination) and will include all assessments of efficacy (ICARS, CGI-C, CGI-S, VABS, and EQ-5D-5L) and safety (vital signs [including weight and height in triplicate], ECG, routine laboratory tests, physical and neurological examinations, C-SSRS, BMD and assessments of AEs and concomitant medication use), as well as special laboratory tests [HbA1c, CD4+ lymphocytes count, α -fetoprotein, CRP, and RBC antibodies (IgG, IgM, Qualitative Direct Coombs test)]. A serum and urine pregnancy test will be performed for women of childbearing potential. The efficacy evaluations at Visit 9 will be used as Endpoint assessments for statistical purposes. The final blood sample (trough level) for the dexamethasone PK analysis will also be collected. The total volume of blood collected throughout the 6-month study for all PK samples would be approximately 42 mL.

Extension Treatment Period (6 months)

Patients completing the 6-month Initial Treatment Period and doing well on the study medication will be eligible for continuing treatment for an additional 6 months in the Extension Treatment Period. Informed

Version 1.0, 09May2015; Version 2.1, 16Nov2015; Version 3.0 (Amend. 1), 01Feb2016; Version 3.1 (Amend. 2), 28Apr2016; Version 3.2 (Amend. 3), 25May2016; Version 4.0 (Amend. 4), 29Nov2016; Version 5.0 (Amend. 5, Site-specific), 20Sep2017; Version 6.0 (Amend. 6), 29Sep2017; Version 7.1 (Amend. 7.1), Final 13 March 2018, Version 8.0 (Amend. 8.0), Final 23 April 2018; Version 10.0 (Amend. 10), Final 16 April 2019; Version 11.0 (Amend. 11), Final 24 Jun 2020

consent/assent must be obtained in writing for the extension, as in the Initial Treatment Period. Patients meeting all entry criteria will be treated as follows:

- Patients originally randomized to one of the two dose ranges of EDS (Groups 1 or 2) will continue on the same treatment;

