12 EFFICACY EVALUATIONS

12.1 ICARS

12.1.1 *Description of the ICARS*

The primary efficacy endpoint in the AT study will be the mean change from baseline to endpoint (Month 6 or early discontinuation) in the total score on the ‘Modified’ International Cooperative Ataxia Rating Scale (ICARS).

The ICARS (Trouillas et al, 1997), the most frequently used clinician-(neurologist) rated measure in patients with ataxias, was developed by a Committee of the World Federation of Neurology to help standardize common manifestations of syndromes that lead to cerebellar dysfunction. The ICARS is a 100-point, semi-quantitative scale offering a compartmentalized quantification of the following 4 sub-scores: Posture and Gait Disturbances (34 points), Kinetic Functions (52 points), Speech Disorders (8 points), and Oculomotor Disorders (6 points).

The complete ICARS will be rated in the current study; however, for the primary efficacy endpoint, the ‘Modified’ ICARS will be used. The ‘Modified’ ICARS excludes all of the Oculomotor Disorders items (items 17-19) and items 8-12 in the Kinetic Functions domain, as these items do not directly contribute to functioning.

12.1.2 *Validity of ICARS in AT Patient Population*

The internal consistency, criterion-related validity, and internal construct validity of the ICARS have been established in patients with focal cerebellar lesions (Schoch B et al, 2007). The inter-rater reliability, test-retest reliability and internal consistency have also been validated in patients with spinocerebellar ataxia (Weyer et al, 2007, Schmitz-Hubsch et al, 2006a). The ICARS total score satisfied all psychometric criteria in a validation study in patients with Friedreich’s Ataxia (Cano et al, 2005; Metz et al 2013). The ICARS has been used as an outcome measure in interventional studies in patients with ataxia, but there are no clinical data to suggest the magnitude of change on the ICARS that would correspond to a clinically relevant improvement, due to the absence of any drug producing such a benefit. The ICARS has been used in several studies in patients with Friedreich’s Ataxia over the age of 8 years, in phase III potentially pivotal trials (Lynch et al, 2010), as well as in open-label long-term studies (Meier et al, 2012).

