Following the testing for the primary endpoint, an ordered hierarchical testing (step-down) of the key secondary endpoint (CGI-C), and other secondary endpoints, i.e. CGI-S, followed by VABS, will be performed, according to the methodology described by [Dmitrienko and D’Agostino \(2013\)](#), as shown in Figure 3.

Version 1.0, 09May2015; Version 2.1, 16Nov2015; Version 3.0 (Amend. 1), 01Feb2016; Version 3.1 (Amend. 2), 28Apr2016; Version 3.2 (Amend. 3), 25May2016; Version 4.0 (Amend. 4), 29Nov2016; Version 5.0 (Amend. 5, Site-specific), 20Sep2017; Version 6.0 (Amend. 6), 29Sep2017; Version 7.1 (Amend. 7.1), Final 13 March 2018, Version 8.0 (Amend. 8.0), Final 23 April 2018; Version 10.0 (Amend. 10), Final 16 April 2019; Version 11.0 (Amend. 11), Final 24 Jun 2020

[figure not shown]

Figure 3. Hierarchical Testing Procedure for Primary and Secondary Endpoints

Secondary endpoints will be tested in the following order (see also Figure 3 flowchart). A sequential testing approach will be used, for which the ~14-22 mg dose versus placebo for the secondary endpoints will be tested in the following order: 1) CGI-C, 2) CGI-S, and 3) VABS. This is to be followed by testing the same secondary variables in the same order for the ~5-10 mg dose versus placebo: 1) CGI-C, 2) CGI-S, and 3) VABS. All tests will be performed at the 0.05 two-sided significance level, and testing will continue to the next variable/dose level only if significance is achieved for the current test.

The analytic approach for these variables will use ANCOVA with missing value imputed using LOCF, OC, and OC + RDO.

The analyses of the EQ-5D-5L will be exploratory.

Efficacy Analysis – Extension Treatment Period

For the Extension Treatment Period, comparisons will be made for the ‘Modified’ ICARS, CGI-S, VABS, and QoL [EQ-5D-5L] using ANCOVA with missing values imputed using LOCF, OC, and OC + RDO.

Analyses for the various randomization periods

The primary analysis will compare the treatment groups as specified in Figure 3 (in the “Primary Testing” panel) after 6 months of treatment. Only these 6-month evaluations will be controlled at the Type I FWER of 0.05 two-sided.

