3.1 Efficacy Endpoints

Initial 6-Month Treatment Period

Primary Efficacy Endpoint

- The change of the Modified International Cooperative Ataxia Rating Scale (mICARS) scores from baseline to Visit 9. The change in the full ICARS from baseline to Visit 9 will be presented as a sensitivity analysis.

Key Secondary Efficacy Endpoint

- CGI-C at Visit 9

Other Secondary Efficacy Endpoints

- The change of CGI-S (structured) score from baseline to Visit 9.
- The change of VABS score from baseline to follow-up based on repeated measures at Visit 6 and Visit 9

Tertiary Efficacy Endpoints

- The change of QOL scores (EQ-5D-5L scale) from baseline to follow-up based on repeated measures at Visit 6 (“Month 3”) and Visit 9 (“Month 6”)

Supplemental Analysis

The modified ICARS will be rescored, using two separate methods, collapsing categories within specific items. Each method will result in a smaller total sum score across the ICARS domains. These will be referred to as Rescored mICARS Method 1 (key opinion leader [KOL] suggested) and Rescored mICARS Method 2 (CCI definition), to prevent confusion with modified ICARS. Details of the mapping to each of these abbreviated scales are presented in [Appendix II](#) and [Appendix III](#), respectively, of this document.

Extension Treatment Period (Months 6 to Month 12 of the study)

For the Extension Treatment Period, comparisons will be made for the ‘Modified’ ICARS, CGI-C, CGI-S (structured), VABS, and QoL [EQ-5D-5L] using the same methods as for the initial treatment period with missing values imputed in the same way. In addition, the full ICARS, Rescored mICARS Method 1, and Rescored mICARS Method 2 will be evaluated using the same methods as the modified ICARS.

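### The deciding test names no visit, the stated power does not describe a Visit 9 test, and the low-dose gate differs between protocol and SAP

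*SAP*

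**What the plan says.** **Timepoint.** SAP 3.1 defines the primary endpoint as "The change of the Modified International Cooperative Ataxia Rating Scale (mICARS) scores from baseline to Visit 9". Protocol 7.3 agrees ("The primary efficacy endpoint will be at the 6-month assessment"), as do footnote a of the visit schedule ("Efficacy evaluations on Month 6 (Visit 9) will be used as the Endpoint assessments for all efficacy measures"), Protocol 11.2 and Protocol 12.1.1. Protocol 16.2.8 confines error control to Month 6: "Only these 6-month evaluations will be controlled at the Type I FWER of 0.05 two-sided". Against these, the formal endpoint definitions in Protocol 16.1 and 16.2.7 give change from baseline at Days 90 and 180.

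SAP 5.3.1 models Visits 6 and 9 together with treatment, visit and their interaction, and then writes "The treatment effect, together with the associated two-sided 95% CI and p-value will be calculated". No visit is attached. The matching sentence in Protocol 16.2.8 and the hypotheses in SAP 5.1.10 do not attach one either. A visit does appear for the supporting work: "Sensitivity analyses of these primary analyses will consist of ANCOVA at Visit 9".

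**Power.** Protocol Table 4 and SAP Table 3 give 20 powers for 54 per group at two-sided 0.05. Differences run from 3.0 to 3.7 and SDs from 5.0 to 8.0. The text cites two repeated measures and a PASS repeated-measures module, and calls power sufficient for SD 5.0 to 7.0. No correlation or covariance pattern is given. SAP 5.1.7 adds that the sample size keeps at least 80% power for the full ICARS.

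**Gate.** Protocol 16.2.1, 16.2.7 and 16.2.8 open the low-dose mICARS test once high-dose mICARS is significant. SAP 5.1.7 and 5.1.10 also require the high dose to succeed on CGI-C. Protocol 16.2.8 tests CGI-S and VABS in the 0.05 sequence after CGI-C; SAP 5.1.10 does not mention them. SAP 5.10, which records changes from the protocol, covers only the dropped retrieved-dropout analysis and visit timing.

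**The concern.** With a treatment-by-visit term in the model, the treatment effect can be the Visit 9 difference or the average over Visits 6 and 9. SAP 5.1.10 and 5.8 rest the success of the trial on this one p-value. A reader working from Protocol 16.1 and one working from SAP 3.1 could compute different contrasts, and a choice settled after unblinding would be open to doubt.

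The power figures matter for reading a negative result. If the Visit 9 test has much less power than stated, a non-significant result is weaker evidence of no effect than the plan suggests.

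If the high dose succeeds on mICARS and fails on CGI-C, the protocol says to test the low dose and the SAP says not to. Whether CGI-S and VABS can support an error-controlled claim is also undefined.

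**Working it through.** **Reproducing the table.** Inputs from Protocol 16.2.1 / SAP 5.1.7: n = 54 per arm, two-sided 0.05. Normal approximation: SE = SD × √(2f/54), power ≈ Φ(difference/SE − 1.96), where f is the fraction of the single-visit variance retained.

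- Difference 3.0, SD 7.0, f = 0.5: SE = 0.953, z = 3.149, power 88.3%. This is the stated figure.
- f = 0.50 reproduces all 20 cells to the printed decimal; f = 0.495 matches 7 and f = 0.505 matches 6.

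**What f = 0.5 means.** For the average of two visits with correlation ρ between the two changes, f = (1 + ρ)/2, so f = 0.5 needs ρ = 0. For Visit 9 alone with covariate correlation r, f = 1 − r², so f = 0.5 needs r = 0.71. Given the module named, zero between-visit correlation is the natural reading, although the two changes share one baseline. Neither assumption is stated.

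**Power at 3.0 / SD 7.0, 54 per arm**

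| Test | Assumption | f | Power |
|---|---|---|---|
| As stated | – | 0.50 | 88.3% |
| Visit 9 | no covariate gain | 1.00 | 60.5% |
| Visit 9 | r = 0.20 to 0.29 | 0.96 to 0.92 | 62.2 to 64.3% |
| Visit 9 | r = 0.5 (assumed) | 0.75 | 73.0% |
| Two-visit average | ρ = 0.4 (assumed) | 0.70 | 75.9% |
| Two-visit average | ρ = 0.8 (assumed) | 0.90 | 65.1% |

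Reaching 80% at Visit 9 in this cell needs r = 0.61.

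**Where r = 0.20 to 0.29 comes from.** Protocol 7.1.3.1 gives a Phase II baseline ICARS SD of 12.8. Protocol 16.2.1 gives an SD of 5.0 to 7.4, read here as the SD of change because it is far below 12.8. With equal SDs at baseline and Month 6:

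- Raw correlation = 1 − SDc²/(2 × 12.8²) = 0.924 (SDc 5.0) or 0.833 (SDc 7.4).
- |corr(baseline, change)| = √((1 − raw)/2) = 0.195 or 0.289.

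If the Month 6 SD is 10% below 12.8, r is 0.44 to 0.45 and power 69.8 to 70.5%. If it is 10% above, r is 0.07 to 0.11 and power 60.8 to 61.0%.

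**Across the table.** Of the 15 cells called sufficient (SD 5 to 7), a Visit 9 test falls below 80% in 7 with no covariate gain, in 5 or 6 at r = 0.20 to 0.29, and in 2 at r = 0.5. Every SD 5 cell stays at 87.7% or more.

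**Full ICARS, 3.7 / SD 7.4.** The table's method gives 95.7%. Visit 9 gives 73.8% with no covariate gain, 75.5 to 77.5% at r = 0.20 to 0.29, and 85.1% at r = 0.5; 80% needs r = 0.37.

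**How often the two contrasts disagree on significance.** By simulation, assuming equal effects at both visits and ρ from 0.8 to 0.4: 10 to 21% of trials at 3.0/SD 7, 9 to 17% at 3.0/SD 6, 5 to 10% at 3.0/SD 5, 5 to 9% at 3.7/SD 6, and 2 to 3% at 3.7/SD 5.

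**Gate.** These figures are illustrative, since the documents give no CGI-C or low-dose power. Assumed inputs are low-dose power 0.5 to 0.8, correlation 0.5 between dose contrasts, and correlation 0.3 to 0.5 between CGI-C and mICARS. The share of trials in which the SAP blocks a low-dose claim that the protocol allows is:

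| High-dose mICARS power | CGI-C power 80% | CGI-C power 50% |
|---|---|---|
| 60.5% | 4 to 8% | 13 to 23% |
| 88.3% | 6 to 13% | 19 to 34% |

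**The case against.** On timepoint, SAP 3.1 gives VABS and EQ-5D-5L as repeated measures at two visits but puts mICARS at Visit 9, so its authors distinguished the two forms. The sensitivity ANCOVA at Visit 9 is to be compared with the primary model, which implies the same visit there. No passage names a two-visit average as the contrast, and the blinded programs or mock tables, which are not part of these documents, may fix it. This makes Visit 9 the likely intention, but the sentences that generate the p-value still do not say so and two formal definitions say otherwise.

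On power, the two repeated measures and the software module are disclosed; only the correlation is missing. The range r = 0.20 to 0.29 rests on equal SDs, full ICARS rather than mICARS, 22 single-arm patients, and baseline as the only covariate, whereas the SAP model also has age, sex and region. A Month 6 SD 10% lower lifts full-ICARS power at 3.7/7.4 to about 82 to 83%, so the SAP's 80% claim could hold. That limits the Phase II estimate and leaves the full-ICARS point open, but even r = 0.5 leaves the 3.0/7.0 cell at 73.0%. It is also fair that the confidence interval, rather than planning power, should carry the reading of a negative result, and that restating power changes no test.

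On the gate, the SAP's sequence is stricter, pre-specified and internally consistent, and error control and trial success are unaffected. The defect is the unlisted conflict between documents and the unstated role of CGI-S and VABS.

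**Conclusion.** All three points hold and should be settled before unblinding.

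- **Timepoint.** The confirmatory contrast is not fixed by the text, and Protocol 16.1 and 16.2.7 conflict with the rest of the plan. Most passages support Visit 9.
- **Power.** The table is not an arithmetic slip, but it depends on an unstated assumption and overstates the power of a Visit 9 test. At 3.0/7.0 the figure is 60.5% with no covariate gain, and roughly 61 to 70% over the Phase II-based range with the Month 6 SD varied by 10% either way, against 88.3%. The size of the shortfall rests on the limited Phase II figures; the mismatch itself does not. With SD near 5 the trial remains well powered.
- **Gate.** The two documents give opposite instructions when high-dose mICARS succeeds and CGI-C fails. The protocol side is read from its text only, because Figure 3 is not shown.

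**What to change.** Before unblinding:

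1. State in SAP 5.3.1 and 5.1.10 and in Protocol 16.2.8 that the confirmatory test is the high-dose minus placebo difference in least-squares mean change in mICARS at Visit 9, taken from the treatment-by-visit term. Make Month 3 and the two-visit average supportive, and align Protocol 16.1 and 16.2.7.
2. Restate power for that contrast with the covariate and between-visit correlations assumed, and correct or re-derive the full-ICARS sentence in SAP 5.1.7.
3. Write one gatekeeping sequence in both documents and say whether CGI-S and VABS are inside it or nominal.
4. List these changes in SAP 5.10.

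The cost is wording and a lower stated power; no new data are needed. Enrolment closed at 175, so the power cannot be recovered with more patients. Under Protocol 17.2, protocol edits that are not administrative need ethics approval; SAP text and a 5.10 entry could carry much of the correction.
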